**Design & Procedures** 

Describe the study, providing details regarding the study intervention (drug, device, physical
procedures, manipulation of the subject or the subject's environment, etc.). Discuss justifications for
placebo control, discontinuation or delay of standard therapies, and washout periods if applicable.
Identify procedures, tests and interventions performed exclusively for research purposes or more
frequently than standard of care. Include alternative therapies, concurrent therapies discontinued per
protocol, risk benefit ratio, and use of tissue/specimens. Discuss monitoring during washout periods if
applicable. Include brief description of follow-up, if any.

This individually randomized, group-treatment feasibility and efficacy trial will compare the *Labda Siku Moja* internalized stigma intervention to treatment as usual (TAU). Treatment as usual will consist of routine care offered by each site; currently, there is no specific stigma reduction intervention delivered as part of routine care in Tanzania. Specifically, feasibility will utilize a process evaluation approach while efficacy and determination of effect sizes will utilize a 2x4 repeated measures randomized controlled trial (2 treatments x 4 time points [baseline, 30 days, 90 days, 180 days]) with a post-intervention focus group "to expand our understanding of how best to deliver the intervention, it is crucial to include the voices of the participants in the evaluation of the intervention" as advocated by Ma et al.. By conducting a post-intervention focus groups, we can "elicit the participants' experiences with the intervention, and how to further improve it.34, p. 739.

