**Intervention Procedures.** Before implementing the intervention, we will work with the Community and Technical Advisory Board (CTAB) to finalize all study procedures. The CTAB will consist of 6 to 8 individuals and will be co-chaired by a social/ behavioral scientist experienced in HIV research, [name], and a national HIV community advocate, [name], Program Coordinator and Co-Founder, Kimara Peer Educators and Health Promoters (please see letters of support). Other CTAB members may include health center or dispensary staff, a representative from TACAIDS and/or the National AIDS Control Program/ MOH, and at least one WLWH. This CTAB will provide guidance on all study and human subjects protection procedures and will help identify mechanisms to recruit WLWH who may be disconnected from care.

The intervention will be delivered via in-person groups. These groups will be held at either the dispensary or health center where the WLWH were recruited or at MUHAS. Regardless of site, the group/cohort meetings will occur in a private room. The stories of the *Labda Siku Moja* intervention will be viewed on either a health facility/dispensary TV or projected from a laptop using existing equipment. During the 5 weekly meetings, intervention arm participants will view one story and have a structured debrief by the Tanzania MPI; the structured debrief will use Motivational Interviewing (MI), a practical, empathetic, and short-term process that recognizes the difficulty of making life changes. MI utilizes a spirit of empathy, acceptance, respect, honesty, and caring, which helps in building warm, trusting relationships. MI will help the participants in the intervention arm of this study to explore and resolve issues, feelings, and insecurities associated with HIV-related stigma.

The recruited sample recruited will be comprised of both **urban and rural Tanzanian WLWH,purposivel y stratified by age (18-24/25+)**. Eligible participants will be individually randomized in 8 waves (8 waves x 10 participants/wave x 2 sites (urban site and rural site) yielding the sample of 160 participants (80 intervention arm and 80 control arm). Up to 200 may be consented to factor in for screen failures.

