#### STATISTICAL DESIGN AND POWER

**Power Analysis.** The proposed study is designed to assess the preliminary efficacy of the intervention and to generate pilot data to support the conduct of a larger trial. The sample size of 160 is, therefore, primarily determined by whether the intervention could be feasibly implemented in a larger, multi-site study and to calculate a pooled effect size for the primary outcomes so as to determine the sample size necessary for such a large study, rather than by the power to detect specified effect sizes. Nevertheless, we have conducted a power analysis using the Optimal Design for mixed effects models on repeated measures of continuous outcomes, employing an intention-to-treatment analysis. The power analysis revealed that a total sample size of 160 (i.e, 80 in each treatment arm) would achieve 80% power to detect a standardized effect size  $\delta$  of 0.51 with four repeated measurements, assuming an intra-class correlation of 0.70 and a two-tailed alpha of .05. The standardized effect size  $\delta$  is analogous to Cohen's d for which Cohen defines 0.20 as a small effect, 0.50 as a medium effect size, and 0.80 as a large effect. Thus, we will have sufficient power to detect a medium effect size of the longitudinal intervention effect on a linear trend of stigma, coping self-efficacy, and self-esteem over time. For comparing intervention effects at days 30, 90, and 180, cross-sectionally, the results from another power analysis with the  $G^*Power^{49}$  on independent-sample tests show that we will have 80% power to detect a close to medium effect size of Cohen's d = 0.45. Additionally, we expect the dropout rate will be less than 10% based on studies we have conducted in this area, and attrition between conditions will not differ. The sample size will not require an attrition adjustment because mixed-effects models allow for data missing at random.

**Statistical Analysis, Aim #1, Feasibility:** To assess the feasibility, the following parameters will be collected and evaluated:

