Statistical Analysis, Aim #2: We will conduct an intention-to-treat analysis which will include all women randomized to determine whether women living with HIV who viewed the video experience a greater reduction in internalized stigma and greater improvements in coping self-efficacy and self-esteem over the 180 days than women in the control condition. Two-tailed statistical tests will be performed using SAS 9.4. For this exploratory study, the significance level will not be adjusted for multiple tests. Student *t*-tests and chi-square tests will be used to test whether the randomization balanced the conditions on key baseline characteristics and baseline scores on the main outcomes. If treatment conditions differ significantly on any these characteristics, which is unlikely to happen though due to the random assignment, the baseline measure would be controlled as a covariate in subsequent analyses. Random coefficients regression models (a type of hierarchical mixed effects model for repeated measures) will be used to examine between-condition differences in change over time (trajectories across baseline, 30 days, 90 days, and 180 days) in the outcomes. Fixed effects will be condition, time, and condition-by-time, while random effects will be participant and participant-by-time. If necessary, baseline covariates will be included as fixed effects. We will also conduct a priori contrasts to examine differences between treatment conditions at 30, 90, and 180 days. Observed effect sizes will be calculated for the condition-by-time effects (rate of change) and between-condition differences at 30, 90, and 180 days.

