## Time/Accrual Rate.

In accordance with the study timeline, we will recruit participants beginning in Year1/Month 6 and follow participants through Year 2/Month 9. Control and intervention eligible participants will be individually randomized in 8 waves (8 waves x 10 participants/wave x 2 sites (urban site and rural site) yielding the sample of 160 participants (80 intervention arm and 80 control arm). We estimate that it will take 6 months to complete recruitment.

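### The intervention is delivered in groups, but neither the Aim 2 model nor the power figures contain a group effect, so precision and power are overstated if outcomes within a group are correlated

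*Combined protocol and SAP*

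**What the plan says.** The Design & Procedures section names the design itself: "This individually randomized, group-treatment feasibility and efficacy trial will compare" the intervention with treatment as usual. Under Intervention Procedures, "The intervention will be delivered via in-person groups", with five weekly meetings. On location, "These groups will be held at either the dispensary or health center where the WLWH were recruited or at MUHAS". At each meeting "intervention arm participants will view one story and have a structured debrief by the Tanzania MPI". No groups are described for the control arm.

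The section Time/Accrual Rate gives the enrolment structure: "Control and intervention eligible participants will be individually randomized in 8 waves (8 waves x 10 participants/wave x 2 sites", making 160 women, 80 per arm. Treatment-group size is not stated anywhere.

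The Aim 2 paragraph under Statistical Design and Power lists the model terms: "Fixed effects will be condition, time, and condition-by-time, while random effects will be participant and participant-by-time". The only additions it allows are baseline covariates.

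The Power Analysis paragraph makes two claims. For the linear trend, "a total sample size of 160 (i.e, 80 in each treatment arm) would achieve 80% power" at a standardized effect of 0.51, with four repeated measurements and an intra-class correlation of 0.70. For the comparisons at days 30, 90 and 180, using tests for independent samples, "we will have 80% power to detect a close to medium effect size of" d = 0.45. Neither claim includes a group ICC or a design effect.

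**The concern.** Women who share five facilitated discussions can influence one another. Randomizing individuals does not remove correlation that arises after randomization, within the groups. If that correlation is positive, the variance between groups is part of the true variance of the treatment difference but not of the standard error that the plan would compute. Confidence intervals are then too narrow, the nominal 5% test rejects too often, and the stated power is not delivered.

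The effect-size estimates remain unbiased; only their stated precision is wrong. That still matters, because the Power Analysis paragraph says the effect sizes will be used to size a larger trial. If that trial keeps the group format it will need a design effect, and the model as written cannot supply one.

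**Working it through.** **Inputs from the documents.** 80 women per arm; two-sided alpha 0.05; d = 0.45 for a single visit; 0.51 for the trend; 10 women per wave and site, 8 waves, 2 sites.

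**Assumptions.** Group ICC of 0.01, 0.05 or 0.10. Group size m is either 5 (16 groups, if each wave and site is split 1:1) or 10 (8 groups, for example if a wave's two sites were combined).

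**Step 1: reproduce the plan's figures.** A two-sample t-test with 80 independent women per arm has 80.8% power at d = 0.45, and the detectable d at 80% power is 0.446. The stated 0.45 therefore assumes independence.

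For the trend, one reading reproduces 0.51: slope variance 0.70, residual variance 1 and four equally spaced times. Reliability is 0.70/(0.70 + 1/5) = 0.778, the noncentrality is 160 × 0.51² × 0.778/4 = 8.09, and power is 80.7%. Two other readings give 76.5% and 86.8%, so the authors should confirm this one. The 0.70 cannot be a treatment-group ICC: used that way, the visit-specific detectable d would be 0.69 (m = 5) or 0.91 (m = 10).

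**Step 2: add clustering in the intervention arm only.**
- Design effect in that arm: DE = 1 + (m − 1) × ICC.
- True variance of the arm difference relative to the ungrouped value: R = (1 + DE)/2.
- Type I error of the ungrouped test: 2 × [1 − Φ(1.96/√R)].
- Power of a group-aware test: noncentral t with noncentrality d/√(2R/80) and Satterthwaite degrees of freedom (DE + 1)²/[DE²/(k − 1) + 1/79], where k is the number of groups.

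Example for m = 5 and ICC 0.05: DE = 1.20 and R = 1.10, so type I error is 2 × [1 − Φ(1.96/1.049)] = 6.2%.

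| Layout | ICC | R | Type I error, ungrouped test | df | Power at d = 0.45 | Detectable d |
|---|---|---|---|---|---|---|
| 16 × 5 | 0.01 | 1.020 | 5.2% | 49 | 79% | 0.456 |
| 16 × 5 | 0.05 | 1.100 | 6.2% | 45 | 76% | 0.475 |
| 16 × 5 | 0.10 | 1.200 | 7.4% | 40 | 72% | 0.497 |
| 8 × 10 | 0.01 | 1.045 | 5.5% | 24 | 76% | 0.472 |
| 8 × 10 | 0.05 | 1.225 | 7.7% | 19 | 68% | 0.517 |
| 8 × 10 | 0.10 | 1.450 | 10.4% | 16 | 60% | 0.568 |

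Simulation with 40,000 null trials per cell agrees: 5.2%, 6.1%, 7.4% and 5.6%, 7.6%, 10.4% for the ungrouped test, and 4.9% to 5.3% for the group-aware test. At ICC 0.01 most of the power loss is the degrees-of-freedom cost of having few groups, which the plan does not count either.

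**Step 3: the trajectory test.** Generalized least squares was run with times 0, 1, 3 and 6 months, 16 groups of 5, and illustrative variances: participant 0.70, residual 0.30, participant slope 0.005.
- Group-intercept variance of 0, 0.1 or 0.3: the condition-by-time standard error stays at 0.0220.
- Group-slope variance of 0.0005 or 0.001: it rises to 0.0227 or 0.0233.
- Group variance arising after baseline of 0.05 or 0.10: it rises to 0.0227 or 0.0231 with optimal weights, and to 0.0229 or 0.0239 with the weights of the planned ungrouped model.

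The condition-by-time test is therefore affected only by group differences in change. Scaled to 80% power without clustering, the last pair gives Φ(2.80 × 0.0220/0.0229 − 1.96) ≈ 77% and Φ(2.80 × 0.0220/0.0239 − 1.96) ≈ 73%, before any degrees-of-freedom penalty. If instead the assumed ICC applied directly to women's slopes, the R and df of Step 2 give 78%, 75% and 71% (16 × 5) or 75%, 68% and 59% (8 × 10).

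**The case against.** The omission itself is not in dispute; the case on the other side concerns its size.

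- **Layout.** Ten women per wave and site with 80 per arm overall points to about 5 intervention women per wave and site. Eight groups of 10 would require pooling sites or merging waves, which the documents do not describe. This stands: 16 × 5 is the better-supported layout and 8 × 10 is an upper case. Allowing sessions at MUHAS makes 8 × 10 possible, no more.
- **ICC.** One role leads the debriefs and every group sees the same stories, so there is no between-facilitator variation. This also stands and argues for a low ICC, but it does not remove peer effects within a group.
- **Visit contrasts.** The type I errors in Step 2 come from a two-sample comparison at one visit. If the contrasts are taken from a model with linear time, the error varies by visit: under the illustrative variances, 16 × 5 and post-baseline group variance of 0.05, it is nearer 5.5% at day 30 and above 6% at day 180. The plan does not say how the contrasts are computed, so the tabled values apply to the single-visit reading.
- **Scale against other losses.** With 72 women per arm, the plan's own 10% dropout ceiling, power at d = 0.45 is already 76.5%. That is a similar loss to 16 × 5 at ICC 0.05, but it adds to the group effect rather than replacing it.
- **Purpose.** The study is exploratory and its size was not set by power. This limits the severity. The plan nevertheless specifies two-tailed tests, claims sufficient power, and passes its effect sizes to a larger trial.
- **Estimability.** At a true ICC of 0.05 its standard error would be about 0.09 (16 × 5) or 0.08 (8 × 10). An estimate of 0.05 would have a 95% interval of about −0.08 to 0.30 or −0.04 to 0.35. The estimate will be imprecise and must be reported as such. The group term is still needed for valid standard errors.

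**Conclusion.** The concern holds. The random-effects list is complete as written and has no group term, the power figures have none, and no other section supplies one.

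The consequence is conditional on positive within-group correlation and, for the trajectory test, on groups differing in change after baseline. For 16 groups of 5 and an ICC of 0.01 to 0.05, the effect on a visit-specific comparison is modest: type I error of 5.2% to 6.2%, and a detectable d of 0.456 to 0.475 instead of 0.446. At 8 groups of 10 and an ICC of 0.10 it is substantial: 10.4% and 0.568. ICC and group size are both assumed. Because the aim is exploratory, this should be fixed but does not invalidate the study.

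**What to change.** 1. Replace the Aim 2 model with a partially nested one that has random effects for treatment group in the intervention arm only. Include group-by-time, or a group effect acting after baseline; a group intercept alone leaves the condition-by-time standard error unchanged. Use Satterthwaite or Kenward-Roger degrees of freedom, which the planned SAS 9.4 can do. Prespecify a simpler form in case the model does not converge with 8 to 16 groups.
2. State the planned group size and how women are assigned to groups. Record the assigned group at randomization for every intervention woman, including those who never attend. The session attendance rosters described under Purpose of the Study (Fidelity) do not cover the intention-to-treat set.
3. Report the group ICC with its confidence interval, say that it is imprecise, and have the larger trial plan over a range.
4. Restate the detectable effects in the Power Analysis paragraph over a stated range of ICC and group size, and say how the visit contrasts are computed.

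The cost is SAP wording, the extra random-effect terms, one recorded field and a slightly less favourable stated detectable effect. No further participants are needed. The group field should be settled before randomization, because it may not be recoverable later for women who never attend.

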In Tanzania, where 80% of the population lives in rural areas and HIV is the third leading cause of death, an estimated 880,000 women are living with HIV. In sub-Saharan Africa, including Tanzania, WLWH contract HIV at least 5 to 7 years earlier than men because they are more likely to have older partners, get married earlier, and have greater challenges in negotiating safer sex because of gender inequality. In 2018, according to UNAIDS, 4.6% of Tanzanian adults between the ages of 15 and 49 were living with HIV with the **prevalence being higher among women** (Q = 6.0%:  $3=3.6\%)^{26}$ . Although the prevalence is higher in urban areas (urban, 7.5% versus rural, 4.5%), this study will also recruit rural WLWH since most of the Tanzanian population live in rural areas. Further, one could argue that the Labda Siku Moja intervention may be even more useful for women in isolated, rural areas, as they would have fewer opportunities to see women as portraved in the stories. There are **dispr** oportionate rates of new infections among young women in Tanzania (ages 15-24) compared to their male counterparts of the same  $age^{26}$ . In 2012, women aged 23-24 were twice as likely to be living with HIV as men of the same age. Data from the representative 2016-2017 Tanzania Impact Survey identified that women between the ages of 15 and 39 are more than twice as likely to be living with HIV as their male counterparts. Additionally, the highest HIV prevalence rate in Tanzania is among women aged 45-49, at 12% (compared with 8.4% among men of this age). Thus, in the design of this proposed study, we are focusing on WLWH since they are disproportionately impacted and will purposively recruit based on geography (urban and rural) and age (18-24 and 25+).

The United Republic of Tanzania's *Fourth Health Sector HIV and AIDS Strategic Plan (HSHSP- IV) 2017-*2022 calls for the elimination of HIV related stigma and discrimination recognizing its negative impact on PLWH; and achieving the 90-90-90 targets (now the 95-95-95 targets for 2030). The most recent Tanzanian *PLWH Stigma and Discrimination Survey* (2013; N = 2205, 57% of sample = WLWH) documented that:

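### The Aim 2 model omits site, within which women are randomized in waves, and age band; its covariate rule would exclude a balanced site even when site predicts the outcome

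*Combined protocol and SAP*

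**What the plan says.** All references are to the combined protocol and SAP.

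- **Randomization layout** (Design & Procedures, repeated under Study Sample Recruitment and the accrual sections): "Eligible participants will be individually randomized in 8 waves (8 waves x 10 participants/wave x 2 sites (urban site and rural site". This gives 8 x 10 = 80 women per site, 160 in total, 80 per arm. The split between arms within a site or wave is not stated.
- **Recruitment** (Background & Significance): the team "will purposively recruit based on geography (urban and rural) and age (18-24 and 25" and over). The recruitment sections call age a purposive stratum within a convenience sample. No section says that randomization is stratified by age.
- **Efficacy model** (Statistical Analysis, Aim #2): "Fixed effects will be condition, time, and condition-by-time, while random effects will be participant and participant-by-time". There is no site or age term. The arms are compared on key baseline characteristics with t-tests and chi-square tests, and a characteristic is added as a covariate only if the arms differ significantly on it. The section does not say whether site and age band are among those characteristics.
- **Feasibility** (Statistical Analysis, Aim #1): recruitment, retention, measurement and fidelity metrics are listed without mention of a breakdown by site or age.

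**The concern.** The analysis does not follow the randomization. Where women are allocated within sites, site belongs in the model by design, whatever a baseline test shows. The Aim 2 rule instead asks whether the arms happen to be imbalanced. That is the wrong question for precision: a covariate helps because it predicts the outcome, and a factor balanced by the layout can still do so strongly.

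What is at stake is the width of the confidence intervals for the contrasts at days 30, 90 and 180. The trial exists to supply effect sizes for planning a larger study, so needlessly wide intervals have a cost. The rule also leaves the final model unknown until the baseline data are seen.

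**Working it through.** **Inputs.** From Statistical Design and Power: 80 women per arm, two-sided alpha 0.05, 80% power, d = 0.45 at a single visit, and 0.51 for the linear trend with an intra-class correlation of 0.70. From the randomization layout: 80 women per site. Assumed: the share of outcome variance R² explained by site and age band (5%, 10%, 20%), and 40 women per arm within each site.

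**1. The plan's own figures.** For the visit contrasts the plan says "we will have 80% power to detect a close to medium effect size of Cohen's d = 0.45". In SD units:
- SE = sqrt(2/80) = 0.158.
- Power at 0.45 = Φ(0.45/0.158 − 1.96) = 0.81.
- Detectable d at 80% power = (1.960 + 0.842) x 0.158 = 0.443.

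The figure reproduces. The trend figure also reproduces under one reading of the intra-class correlation, which is an assumption: slope variance 0.70, residual variance 1, four equally spaced visits (sum of squares 5). Then 0.443 x sqrt((0.70 + 1/5)/0.70) = 0.502, against the stated 0.51. Other readings give 0.32 to 0.53. Both of the plan's figures are for the comparison without site or age terms.

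**2. What the covariate rule does to site.** If each wave of 10 is split evenly within site, each site has 40 v 40. The chi-square statistic for arm by site is then 0, and site cannot enter. If allocation is not balanced by site, a test at 0.05 would admit site about 1 time in 20 by chance. In neither case does entry depend on whether site predicts the outcome.

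**3. Precision of the visit contrasts.** The SE after adjustment is approximately sqrt(1 − R²) times the SE before it. The detectable d shrinks by the same ratio, and the unadjusted sample with equal precision is 160/(1 − R²).

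| R² (assumed) | SE ratio | Reduction in SE | Detectable d (from 0.443) | Equivalent unadjusted N |
|---|---|---|---|---|
| 5% | 0.975 | 2.5% | 0.432 | 168 |
| 10% | 0.949 | 5.1% | 0.420 | 178 |
| 20% | 0.894 | 10.6% | 0.396 | 200 |

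**4. The condition-by-time slope.** The trend formula in step 1 contains slope variance and residual variance but no intercept variance. Site and age main effects explain differences in level, so they add little to the slope comparison. Only the interactions with time can help, and only if trajectories differ by site or age.

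**5. What site-specific estimates could show.**
- All women: 1.96 x sqrt(2/80) = ±0.31 SD.
- One site, 40 v 40: 1.96 x sqrt(2/40) = ±0.44 SD (±0.46 at 36 v 36, that is, with 10% dropout).
- Difference in effect between sites: 0.438 x sqrt(2) = ±0.62 SD.
- Power for a between-site difference in effect of 0.45 SD is about 30%. The difference detectable with 80% power is 2.802 x 0.316 = 0.89 SD.

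**The case against.** The strongest reply is that the plan wants a pooled effect size, states no objective or hypothesis about site or age, and lets covariates in when needed. No bias, inflated error rate or contradiction has been shown, and the R² values have no basis in the documents. At 5% to 10% the gain is small, and it hardly touches the slope, which is the main Aim 2 analysis.

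Most of this stands and limits the size of the point. It does not defend the covariate rule. A site-adjusted estimate is still a pooled effect, so the change serves the plan's stated target.

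A reader might also infer several stronger things that the documents do not support:

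- *That the trial randomizes by age band.* Age is a recruitment stratum only.
- *That the trial expects the effect to differ by site and age.* Background & Significance says, as something one could argue, that the "intervention may be even more useful for women in isolated, rural areas". Its other reasons for including rural women and for the age bands are population share and disease burden. It suggests no difference in effect by age.
- *That the trial fails to answer a question it poses.* Effect modification is not a stated aim.
- *That the feasibility metrics will be reported only overall.* The Aim 1 text is silent on breakdown, and attendance and process data are recorded session by session, so tables by site remain possible.
- *That a site interaction would test the rural rationale.* There is one urban district and one or more rural places, so urban/rural is confounded with district and facility. The interval of ±0.62 SD is also too wide.

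**Conclusion.** The point holds as a matter of precision and prespecification. The Aim 2 model leaves out the site within which women are randomized, and its significance-based covariate rule would keep a balanced site out however well it predicts the outcome. The standard errors of the day 30, 90 and 180 contrasts would then be larger than needed. Adjustment would reduce them by about 2.5%, 5% or 11% if site and age band explain 5%, 10% or 20% of variance. Those shares are assumptions, and the gain vanishes if neither factor is prognostic. The slope gains little unless trajectories differ by site or age.

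The statement that site would be balanced assumes a roughly even split within site, which the documents do not spell out. This is a modest improvement at almost no cost; it does not call the validity of the planned analysis into question.

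**What to change.** In Statistical Analysis, Aim #2:

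1. Always include site (urban/rural, as used in the randomization) and site-by-time as fixed effects, regardless of any baseline test.
2. Include age band (18-24/25+) and its interaction with time as a prespecified baseline covariate, described as a recruitment stratum and not as a randomization factor.

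Secondary and optional:

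3. Tabulate the Aim 1 feasibility metrics by site, because the sample size rationale looks to a larger multi-site study. For illustration, with assumed attendance of 95% at one site and 65% at the other and 40 intervention women at each, the pooled figure is (38 + 26)/80 = 80%, which would not show the gap.
4. Give site-specific effects with 95% CIs, labelled descriptive, and note that urban/rural is confounded with district and facility.

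The cost is a few sentences, some extra tables and a few model degrees of freedom: four parameters if time is linear, eight if the four visits are categories. Site and age band are already part of the design, so no extra women, visits or measures are needed.

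### The analysis plan does not say which model or test gives the day 30, 90 and 180 contrasts, and adjusts for baseline scores only if a baseline test is significant

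*Combined protocol and SAP*

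**What the plan says.** The paragraph on Statistical Analysis, Aim #2 names one outcome model: "Random coefficients regression models (a type of hierarchical mixed effects model for repeated measures) will be used to examine between-condition differences" in change over the four measurement times. Its terms are given as "Fixed effects will be condition, time, and condition-by-time, while random effects will be participant and participant-by-time". Whether time is continuous or categorical is not stated.

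The visit contrasts come next: "We will also conduct a priori contrasts to examine differences between treatment conditions at 30, 90, and 180 days". Effect sizes are planned in two kinds. The first is "Observed effect sizes will be calculated for the condition-by-time effects (rate of change"), and the second is the between-arm difference at each of the three follow-up visits. No model, test, time coding or baseline rule is attached to the second kind. Student t-tests appear in this paragraph only as checks of baseline balance. Baseline adjustment depends on those checks: "If treatment conditions differ significantly on any these characteristics", the measure concerned becomes a covariate.

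The Power Analysis paragraph treats the two kinds separately. For the longitudinal effect it says "we will have sufficient power to detect a medium effect size of the longitudinal intervention effect on a linear trend of stigma" and the other outcomes. "For comparing intervention effects at days 30, 90, and 180, cross-sectionally", it reports a second calculation, "on independent-sample tests show that we will have 80% power to detect a close to medium effect size" of d = 0.45. It makes no adjustment for attrition, on the ground that mixed-effects models tolerate data missing at random. It also says that the sample size rests mainly on feasibility and on obtaining a pooled effect size with which to size a larger study. It does not define that pooling.

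**The concern.** The visit differences are a planned output of a pilot whose effect sizes are meant to size the next trial, yet their source is open. Two sources can be read from the documents, and each has a weakness.

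- **Separate two-sample tests**, as the power section suggests. These are unbiased whatever the trajectory when data are complete. They ignore the baseline score, and they use only the women seen at that visit, so the plan's missing-data argument does not cover them.
- **The random-coefficients model**, the only outcome model in the analysis paragraph. If time enters as a straight line, all three contrasts are fixed by one baseline gap and one slope. The intervention is five weekly sessions and follow-up runs to day 180, so an early effect that levels off or fades is plausible and would not fit a line.

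As written, the choice can be made after the data are seen. The significance-triggered baseline rule leaves a second choice to the data.

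**Working it through.** **Inputs from the Power Analysis paragraph:** 80 women per arm, two-sided alpha 0.05, intra-class correlation 0.70, d = 0.45 at each visit. The visits are at days 0, 30, 90 and 180.

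**Assumptions (not in the documents):** outcome SD 1; 0.70 used as the correlation between baseline and follow-up; complete data; no clustering by intervention group; and the effect trajectories below.

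**1. The plan's own figure.** The two-sample standard error is √(2/80) = 0.158, and 0.45/0.158 = 2.85. Power is Φ(2.85 − 1.96) = 81.2% by the normal approximation and 80.8% by the noncentral t. The stated 80% is reproduced. With 10% lost (72 per arm) the standard error is √(2/72) = 0.167 and power is about 77%.

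**2. Contrasts read off a straight line.** With complete data and a random intercept and slope, the fitted arm difference is the least-squares line through the true differences. The mean day is 300/4 = 75. The deviations are −75, −45, 15 and 105, with sum of squares 18,900. For a true effect of 0, 0.45, 0.45, 0.45:

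- slope = 0.45 × (−45 + 15 + 105)/18,900 = 0.001786 per day
- intercept = 0.3375 − 75 × 0.001786 = 0.204
- day 30: 0.204 + 0.054 = 0.257
- day 90: 0.204 + 0.161 = 0.364
- day 180: 0.204 + 0.321 = 0.525

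The same calculation for other assumed shapes:

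| Shape | True effect, days 30/90/180 | Read off the line |
|---|---|---|
| Plateau from day 30 | 0.450/0.450/0.450 | 0.257/0.364/0.525 |
| Fade to half | 0.450/0.338/0.225 | 0.233/0.260/0.300 |
| Full fade | 0.450/0.225/0 | 0.209/0.155/0.075 |
| Linear growth | 0.075/0.225/0.450 | 0.075/0.225/0.450 |

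The line also creates a baseline gap of 0.20 to 0.24 in the first three rows, where the true gap is zero.

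**3. Precision at day 30.**

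- Two-sample test: √(2/80) = 0.158
- Read off the line, with no random-slope variance: √{(2/80) × [0.70 + 0.30 × (1/4 + 45²/18,900)]} = 0.142
- Adjusted for the baseline score: √{(1 − 0.70²) × 2/80} = √0.01275 = 0.113

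At a true 0.45, the baseline-adjusted contrast has power Φ(0.45/0.113 − 1.96), about 98%, against 81% for the two-sample test.

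**4. Effect on the next trial's size.** Per-arm size for 80% power is 2 × (1.960 + 0.842)²/d² = 15.70/d².

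- Plateau, averaging the three visits: the line gives (0.257 + 0.364 + 0.525)/3 = 0.382 against a true 0.450, so 108 against 78 per arm. The next trial is too large.
- Plateau, using day 180 only: 0.525 against 0.450, so 57 against 78. The next trial is too small.
- Half fade, averaging: 225 against 138. Using day 180 only: 175 against 311.

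The direction depends on a definition that the plan does not give.

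**The case against.** The strongest reply is that the distortion needs two things that the plan never states: linear time, and visit contrasts taken from that line. The power section treats the visit comparisons as a separate cross-sectional analysis. The analysis paragraph also lists visit differences apart from the rate of change. Three contrasts drawn from one line would be largely redundant. Separate visit estimates are therefore a fair reading, and under it the trajectory does no harm. This stands. A reader might infer that the plan commits itself to biased visit contrasts, and the documents do not support that.

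It does not close the gap. The two-sample tests are a basis for power and are not carried into the analysis paragraph. They also give up the baseline score and the missing-data protection.

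Two further inferences are tempting. One is that a linear fit would oversize the next trial (or undersize it). The arithmetic gives either result, depending on what is pooled. The other is that the slope test is weak when an effect fades. That is a property of the slope, which is a legitimate rate-of-change summary and stays in the plan. It is not evidence about the visit contrasts.

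The study is also exploratory and was not sized for power. That limits the severity, but an effect size meant for a later design still needs a defined source.

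**Conclusion.** The point holds as a gap in specification that should be fixed. The source of the day 30, 90 and 180 contrasts is not stated, and baseline adjustment hangs on a significance test. The bias is conditional. It is zero if the effect is linear, if time is categorical, or, with complete data, if two-sample tests are used. If the contrasts come from a straight line and the effect is an early plateau of 0.45, the errors are about −0.19, −0.09 and +0.08 SD at days 30, 90 and 180. The trajectories are assumptions. The documents give no expected shape and do not say whether day 30 counts from enrolment or from the last session.

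The gain from a better method is less conditional: a day-30 standard error of 0.113 against 0.158. It rests on correlation 0.70, complete data and no group clustering, and it comes from baseline adjustment, not from dropping linearity. The trial delivers its intervention in groups and expects some dropout, so the 98% power is an upper guide. Whether a linear fit would make the next trial too large or too small cannot be determined, because the pooled effect size is undefined.

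**What to change.** In Statistical Analysis, Aim #2:

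1. State that the day 30, 90 and 180 contrasts and their effect sizes come from a mixed model with time as a categorical factor, and name the within-woman covariance structure.
2. Adjust that model for the baseline score of the outcome in every case, whatever the baseline tests show.
3. Keep the random-coefficients slope as the rate-of-change summary, and state that its time effect is linear if that is intended.
4. State, before data are seen, which estimate feeds the effect size for the larger trial and how any pooling is done. Which estimate leads is the sponsor's choice.

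The cost is SAP wording and a few more model parameters, with the same data, visits and software. Visit contrasts from this model do not depend on the shape of the trajectory, and they keep the missing-at-random argument that the power section already uses.
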